3.3.4 Withdrawal of patients from therapy or assessments

Patients who do not meet all of the inclusion criteria or who meet one or more of the exclusion criteria will not be randomized, and will be considered screen failures. Screen failure patients may be rescreened once based on Investigator judgment and prior permission from medical monitor of the trial. The primary reason for the screen failure will be recorded on the electronic Case Report Form (eCRF).

All patients have the right to withdraw from the trial at any time without the need to justify their decision. The Investigator has the right to remove patients from the trial for non-compliance or other reasons.

Patients may potentially be withdrawn from trial treatment or from the trial as a whole ("withdrawal of consent") with very different implications, please see Sections 3.3.4.1 and 3.3.4.2 below.

Every effort should be made to keep the randomised patients in the trial: if possible on tretament, or at least to collect important trial data.

Measures to control the withdrawal rate include careful patient selection, appropriate explanation of the trial requirements and procedures prior to randomization, as well as the explanation of the consequences of withdrawal.

If a patient discontinues (drops out or withdraws after randomization) from this trial, the patient will not be replaced.

Clinical Trial Protocol

Page 29 of 105

Proprietary confidential information © 2019 Boehringer Ingelheim International GmbH or one or more of its affiliated companies

The decision to withdraw from trial treatment or from the whole trial as well as the reason must be documented in the patient files and eCRF.

3.3.4.1 Withdrawal from trial treatment

An individual patient is to be withdrawn from trial treatment if:

- The patient wants to withdraw from trial treatment, without the need to justify the decision.
- The patient needs to take concomitant drugs that interfere with the investigational product or other trial medication.
- Lack of efficacy defined as PASI50 not reached at Week 14.
- Development of a toxicity or AE which warrants BI 695501/ Humira[®] discontinuation including but not limited to SAEs or suspected unexpected serious adverse reactions (SUSARs).
- The patient has an AE that is categorized as a serious infection. A serious infection is defined as an infection requiring i.v. antibiotics or meeting the regulatory definition of an SAE (including, but not limited to, systemic fungal infections, HIV, HBV, HCV, TB, infected joint prosthesis).
- The patient can no longer be treated with trial medication for other medical reasons (such as surgery, adverse events, other diseases, or pregnancy).
- If the trial treatment is not in the patient's best interest at the Investigator's discretion. (e.g., severe worsening of psoriasis). The patient will be discontinued from the trial to receive treatment as deemed appropriate by the Investigator.
- The patient has repeatedly shown to be non-compliant with important trial procedures and, in the opinion of both, the investigator and sponsor representative, is not willing or able to stick to the trial requirements in the future.

If a patient permanently discontinues trial medication for any reason (including lack of efficacy), every effort should be made to have the patient return for a safety follow-up visit 10 weeks after the last dose of trial medication.

Given the patient's agreement, the patient will undergo the procedures for early treatment discontinuation and follow-up as outlined in the Flow Chart (SFU Visit) and Section 6.2.3.

For all patients the reason for withdrawal from trial treatment (e.g., AEs) must be recorded in the eCRF. These data will be included in the trial database and reported.

3.3.4.2 Withdrawal of consent for trial participation

Patients may withdraw their consent for trial participation at any time without the need to justify the decision.

This will however mean that no further information may be collected for the purpose of the trial and negative implications for the scientific value may be the consequence. Furthermore it may mean that further patient follow-up on safety cannot opccur.

Clinical Trial Protocol

Page 30 of 105

Proprietary confidential information © 2019 Boehringer Ingelheim International GmbH or one or more of its affiliated companies

If a patient wants to withdraw consent, the investigator should explain the difference between treatment withdrawal and withdrawal of consent for trial participation and explain the options for continued follow up after withdrawal from trial treatment, please see Section 3.3.4.1 above.

3.3.4.3 Discontinuation of the trial by the sponsor

Boehringer Ingelheim reserves the right to discontinue the trial overall or at a particular trial site at any time for the following reasons:

- 1. Failure to meet expected enrolment goals overall or at a particular trial site
- 2. Emergence of any efficacy/safety information invalidating the earlier positive benefit-risk-assessment that could significantly affect the continuation of the trial
- 3. Violation of GCP, the trial protocol, or the contract impairing the appropriate conduct of the trial

The investigator / the trial site will be reimbursed for reasonable expenses incurred in case of trial termination (except in case of the third reason).

3.3.5 Replacement of subjects

In case more than 30% of the patients are not eligible for the primary endpoint analysis, the trial clinical monitor together with the trial pharmacokineticist and the trial statistician are to decide if and how many subjects will be replaced. However the total number of patients recruited will not exceed 350. A replacement patient will be assigned a unique study patient number, and will be assigned to the same treatment as the patient he or she replaces.

Page 31 of 105

Proprietary confidential information © 2019 Boehringer Ingelheim International GmbH or one or more of its affiliated companies

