4.1.3 Method of assigning patients to treatment groups

Once patients have completed screening, have met all the inclusion criteria and none of the exclusion criteria, a pre-treatment call will be made using the IRT system.

The Day 1 pre-treatment call will depend on the trial site procedure. The process for treatment assignment will be different depending on the country and respective trial medication shipping timelines. In countries where trial medication needs to be sent to sites in advance due to long shipping timelines (e.g., cross border shipments), trial medication will be provided to the sites in advance, and patients will be assigned treatment on Day 1. For countries where trial medication can be provided on short notice (short shipping times) a pre-treatment call will be made as described below and trial medication will be shipped. The pre-treatment call might be made 15 days prior to the planned first administration of trial medication.

At the beginning of Week 14, patients with at least a PASI50 response will be randomized to one of two sequences (1:1) to either switching or non-switching arm. At Week 14, the randomization will be stratified by the level of their Week 14 response (\geq PASI50 to < PASI75 or \geq PASI75). Access to the randomization code will be controlled and documented. The block sizes of the randomization will be documented in the clinical trial report (CTR).

Randomization will be performed by the IRT. Patients will be randomized sequentially (the lowest sequentially available randomization number).

Each syringe of trial medication will be labelled with the trial code and a unique medication identification number. The IRT system will be used for the randomization, allocation and supply of trial medication throughout the trial. The IRT will assign each patient a unique medication number. Details on the IRT system will be provided in the ISF.

Page 33 of 105

Proprietary confidential information © 2019 Boehringer Ingelheim International GmbH or one or more of its affiliated companies

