6.2.2 Treatment period(s)

The trial medication will be administered at the site on days when trial assessments will be performed. Trial medication will be administered at Visit 2 (Day 1), at Visit 3 (\pm 2 days), and then every 2 weeks from Visit 4 onward.

The procedures and assessments performed at Visit 2 through Visit 8 are shown in the Flow Chart.

At Visit 9 (the beginning of Week 14), patients with at least a partial response (PASI50) at Week 14 will be randomized to one of two sequences (1:1) according to the stratification factors (see Section 4.1.3 for details).

Other procedures and assessments performed at Visit 9 through Visit 26 are shown in the Flow Chart.

Clinical Trial Protocol

Page 55 of 105

Proprietary confidential information © 2019 Boehringer Ingelheim International GmbH or one or more of its affiliated companies

End-of-Treatment procedures and assessments will be performed at Visit 27 as shown in the Flow Chart.

Safety Follow-up procedures and assessments will be performed at Visit 28 as shown in the Flow Chart.

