7.3 PLANNED ANALYSES

Pharmacokinetic parameters of a patient will be included in the statistical analyses of PK endpoints if they are not flagged for exclusion due to a protocol violation relevant to the evaluation of PK. Whether a protocol violation is considered relevant will be decided no later than in the Data Review Meeting (DRM) prior to the data snapshot. Exclusion of a patient's data will be documented in the CTR.

Relevant protocol violations within the time period critical for primary endpoint evaluation (i.e., from Visit 2 to 18) may be:

Page 57 of 105

Proprietary confidential information © 2019 Boehringer Ingelheim International GmbH or one or more of its affiliated companies

- Incorrect trial medication taken, i.e., the patient received at least one dose of trial medication the patient was not assigned to.
- Incorrect or incomplete dose of trial medication taken.
- Missed doses of trial medication.
- Use of restricted medications with suspected impact on PK.
- Missed plasma samples during the dosing interval from Week 12 to Week 14 or from Week 30 to Week 32:
 - o at two consecutive timepoints during Visits 8a-d and 17a-d
 - o before dosing at Week 12, 14, 30 or 32.

Further criteria that may lead to exclusion of subjects or individual plasma concentrations from the calculation of PK parameters or exclusion of PK parameters from statistical analyses may be specified in the TSAP and in the minutes of the Data Review Meeting.

The PKS includes all patients in the Treated Set (TS, see below) who provide at least one primary PK parameter that was not excluded according to the description above.

All efficacy analyses will be based on the Per Protocol Set (PPS).

The PPS consists of all patients

- who were randomized to double-blinded treatment
- who received at least one dose of double-blinded trial medication, and
- who have all efficacy measures relevant for at least one secondary efficacy endpoint, measured prior to randomization (last non-missing value prior to randomization) and at least once post-randomization.

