7.7 RANDOMISATION

On Day 1, all patients meeting the eligibility criteria will be entered and receive Humira[®] during the run-in phase. At the beginning of Week 14, patients with at least a partial response (PASI50) will be randomized at 1:1 to either receive Humira[®] until Week 48 or alternatively receive BI 695501 and Humira[®] until Week 48. Patients not achieving at least a PASI50 response at Week 14 will be considered as non-responders and will be discontinued from the trial. At Week 14, the randomization will be stratified by the level of their Week 14 response (≥ PASI50 to < PASI75 and ≥ PASI75). Access to the randomization code will be controlled and documented. All persons directly involved in the conduct and analysis of the trial will have no access to the treatment allocation prior to final database lock except for unblinded qualified staff who will prepare and administer trial medication. The block sizes of the randomization will be documented in the CTR.

Page 64 of 105

Proprietary confidential information © 2019 Boehringer Ingelheim International GmbH or one or more of its affiliated companies

8. INFORMED CONSENT, TRIAL RECORDS, DATA PROTECTION, PUBLICATION POLICY, AND ADMINISTRATIVE STRUCTURE

The trial will be carried out in compliance with the protocol, the ethical principles laid down in the Declaration of Helsinki, in accordance with the ICH Harmonized Tripartite Guideline for GCP, relevant BI SOPs, the EU regulation 536/2014, and other relevant regulations.

Standard medical care (prophylactic, diagnostic and therapeutic procedures) remains the responsibility of the treating physician of the patient.

The investigator will inform the sponsor immediately of any urgent safety measures taken to protect the trial patients against any immediate hazard, as well as of any serious breaches of the protocol or of ICH GCP.

The BI transparency and publication policy can be found on the following web page: trials.boehringer-ingelheim.com. The rights of the Investigator and of the sponsor with regard to publication of the results of this trial are described in the Investigator contract.

The certificate of insurance cover is made available to the Investigator and the patients, and is stored in the ISF.

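### Section 3.3.5 places replacement patients in the replaced patient's arm instead of randomizing them, and is not reconciled with the no-replacement rule in Section 3.3.4

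*Protocol*

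**What the plan says.** **Replacement (Protocol Section 3.3.5).** The clause opens with a condition: "In case more than 30% of the patients are not eligible for the primary endpoint analysis". If it is met, the trial clinical monitor, the trial pharmacokineticist and the trial statistician "are to decide if and how many subjects will be replaced". Total recruitment may not exceed 350. Each replacement gets a new patient number and "will be assigned to the same treatment as the patient he or she replaces".

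**No replacement (Section 3.3.4).** "If a patient discontinues (drops out or withdraws after randomization) from this trial, the patient will not be replaced". The sentence has no exception, and neither section refers to the other.

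**Allocation.** Section 4.1.3 describes an IRT list: "Patients will be randomized sequentially (the lowest sequentially available randomization number"). Section 6.2.2 says that Week 14 responders "will be randomized to one of two sequences (1:1) according to the stratification factors". Section 7.7 repeats the rule: "At Week 14, the randomization will be stratified by the level of their Week 14 response". The strata are PASI50 to below PASI75, and PASI75 or better. None of these sections makes an exception for replacements.

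**Eligibility for the primary analysis (Section 7.3).** Violations that may exclude a patient's PK parameters include "Missed doses of trial medication", so a patient can be non-evaluable without leaving the trial.

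**The concern.** A replacement who inherits an arm has not been randomized. Three things follow.

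- The arm is fixed by another patient's failure to be evaluable, which happens after randomization and could differ by arm. Section 1.4 itself raises the theoretical possibility that switching increases immunogenicity and hypersensitivity.
- Nothing requires the replacement to belong to the replaced patient's PASI stratum, so the stratification is not kept for these patients.
- If only some patients are replaced, the protocol does not say which. That unstated choice would set the arm split among the replacements.

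At stake is whether everyone in the primary PK comparison was allocated at random. Separately, a patient who drops out between Weeks 14 and 32 will usually lack the Week 30-32 profile and so falls under both rules: Section 3.3.4 says not replaced, Section 3.3.5 says possibly replaced.

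**Working it through.** **Inputs.** From the Synopsis: about 240 entered, about 80% reaching PASI50, and 10%-15% PK non-evaluable. From Section 3.3.5: trigger above 30%, cap 350. From Section 7.4.1: 170 PK-evaluable patients as the initial and minimum size.

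**The plan's own flow reproduces.** 240 × 0.80 = 192 randomized, or 96 per arm. 96 × 0.90 = 86.4, against the stated 86 evaluable per arm.

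**What the 30% is a share of.** The text does not say. Only a randomized patient has an arm to hand on, so randomized patients are the natural denominator. Counted over entered patients instead, the plan's own rates would give 1 − 0.80 × 0.90 = 28% to 1 − 0.80 × 0.85 = 32% ineligible, and the trigger would lie inside the expected range. That reading is weak, because patients who fail PASI50 are never assigned an arm.

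**How likely the trigger is, on the randomized reading.** 0.30 × 192 = 57.6, so at least 58 non-evaluable patients are needed. With independent patients and true loss rate p, the probability is P(Bin(192, p) ≥ 58):

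| p | Probability | Status of p |
|---|---|---|
| 10% | 7.5e-15 | planned |
| 15% | 7.1e-8 | planned |
| 20% | 0.0005 | assumed |
| 25% | 0.059 | assumed |
| 30% | 0.50 | assumed |

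**How the arm split would follow the losses (assumed rates).** With 40% loss in the switching arm and 20% in the continuous arm, 96 × 0.40 = 38.4 and 96 × 0.20 = 19.2. If all were replaced, 38.4/57.6 = 67% of replacements would go to the switching arm. Overall allocation would be (96 + 38.4)/(192 + 57.6) = 54% to 46%.

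**Illustration of scale, assuming 240 entered and a return to exactly 170.** At the trigger, 192 − 58 = 134 remain evaluable. 170 − 134 = 36 evaluable replacements, and 36/170 = 21% of the set. Section 3.3.5 sets no such target, so this is not a prediction.

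**What randomizing instead would cost.** Take 58 losses split 38/20 (assumed), leaving 58 and 76 evaluable. Adding 36 patients randomized 18/18 gives 76 and 94. Relative variance of the arm contrast against 85/85: (1/76 + 1/94)/(2/85) = 1.011, about 1% more.

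**The case against.** **The sections do not really conflict.** Section 3.3.5 is the later, more specific rule, with a trigger and a team decision, so an ordinary reader would take it as an exception to Section 3.3.4. This largely stands. It is the probable intent, and sites do not decide on replacement. A reader might infer that the trial team has two flatly opposite instructions; the text does not support that. What remains is that neither section states the exception.

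**No bias follows.** The copied slot was itself randomized, the arm does not depend on the new patient's characteristics, and the IRT could copy it without unblinding staff. Uneven losses change how many replacements each arm receives, not by themselves what kind of patients they are. Late, uneven entry would tie arm to calendar time, but the model in Section 7.3.1 has a Stage term as well as continuous log(rPASI). This also stands in the main. The adjustment is only partial, since Stage has two levels, and it does not turn these patients into randomized ones.

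**The clause is almost unreachable.** This is true at the planned loss. But the clause exists for the case in which the plan fails, and its content should be sound in that case.

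**Counts depend on a sample size not in view.** Section 11.2 says that the sample size determination in Section 7.8 was updated after the blinded review, and Section 7.8 is not in the text available here. Section 7.4.1 allows recruitment up to the same 350. At 350 entered, 350 × 0.80 = 280 are randomized, the trigger is 85 or more, and up to 280 − 85 = 195 remain evaluable, above 170 with no room under the cap. This stands: a reader might infer that about 36 replacements will be needed, or that they are sure to fit under 350, and the documents establish neither.

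**Conclusion.** The point holds as a wording defect that should be corrected. Section 3.3.5 fixes a non-random allocation rule that no other section provides for, and it is not linked to the contrary sentence in Section 3.3.4. If the clause is used, randomization no longer covers the whole primary comparison, and the numbers per arm among the additions follow the losses per arm.

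The risk is conditional and small under the plan: 7e-15 to 7e-8 at 10%-15% loss, about 6% at 25%. These figures assume 192 randomized, independent losses and a denominator of randomized patients. A reader might infer that the primary result is biased or that allocation concealment is broken. The documents show neither, because the decision may be not to replace anyone and the code stays in the IRT. No alpha level, power or sample size figure changes.

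**What to change.** 1. In Section 3.3.5, delete the same-treatment sentence. State that any additional patients enter the run-in and, if they respond, are randomized 1:1 by the IRT within Week 14 PASI stratum, as far as the recruitment cap of 350 allows given the sample size then in force.
2. In Section 3.3.4, add to the no-replacement sentence: except as described in Section 3.3.5.
3. In Section 3.3.5, state that the 30% is of randomized patients, assessed blinded and pooled over arms.

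The cost is protocol wording only, since the existing IRT list serves. Final arm sizes may be slightly unequal, with about 1% more variance in the assumed 76/94 example. If recruitment is already at the cap, no patients can be added under either wording.

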4. TREATMENTS

4.1 INVESTIGATIONAL TREATMENTS

The trial medication will be provided by BI.

4.1.1 Identity of the Investigational Medicinal Products

BI 695501 and US-licensed Humira® will be used in this trial. Details of the trial medication are provided in Tables 4.1.1: 1, and 4.1.1: 2.

Table 4.1.1: 1 Test product 1

Substance:	BI 695501
Pharmaceutical formulation:	Solution for injection in prefilled syringe
Source:	BI Pharma GmbH & Co. KG, Germany
Unit strength:	40 mg / 0.8 mL
Posology:	40 mg at Week 14 and Week 16 (2 injections), and every other week from Week 22 to Week 48 in the switching arm (14 injections)
Route of administration:	s.c. injection
Site of administration:	Front of the thighs or abdomen/belly, at least 2 inches (about 5 centimeters) away from the navel

Table 4.1.1: 2 Reference product

Substance:	US-licensed Humira® (adalimumab)
Pharmaceutical formulation:	Solution for injection in prefilled syringe
Source:	
Unit strength:	40 mg / 0.8 mL or 40 mg / 0.4 mL
Posology:	80 mg (loading dose) on Day 1, Week 1 40 mg every other week from Week 2 to Week 12 Continuous US-licensed Humira® arm: 40 mg every other week from Week 14 to Week 48 Switching arm: 40 mg at Week 18 and Week 20 (2 injections)
Route of administration:	s.c. injection
Site of administration:	Front of the thighs or abdomen/belly, at least 2 inches (about 5 centimeters) away from the navel

BI 695501 will be provided as sterile, preservative-free, non-pyrogenic, single-use prefilled glass syringes containing 40 mg of BI 695501 per 0.8 mL. One syringe will be used per injection. The needle cap of the syringe contains dry, natural rubber.

Clinical Trial Protocol

Page 32 of 105

Proprietary confidential information © 2019 Boehringer Ingelheim International GmbH or one or more of its affiliated companies

US-licensed Humira[®] will be provided in sterile, preservative-free, non-pyrogenic, single use, prefilled glass syringes containing 40 mg of adalimumab per 0.8 mL or 0.4 mL of solution. One syringe (40 mg) will be used, except for Week 1 / Day 1, at which 2 syringes (80 mg) will be used.

Any unused product or waste material will be disposed of in accordance with local requirements.

4.1.2 Selection of doses in the trial

In the US and EU, Humira[®] has received health authority approval for the treatment of RA, Crohn's disease, plaque psoriasis, psoriatic arthritis, ankylosing spondylitis, juvenile idiopathic arthritis, Uveitis and Hidradenitis suppurativa. The doses of BI 695501 and Humira[®] selected for this trial are reflective of the approved treatment regimen for plaque psoriasis of Humira[®] (initial dose of 80 mg, followed by 40 mg given every other week starting one week after the initial dose) (R16-0358).

